APPENDIX 8 LABORATORY ABNORMALITIES MANAGEMENT TABLE

Laboratory Abnormalities Management (CK and LDH)		
Grade of Liver Test Elevation	Management	Follow-Up
CK > 10 xULN	
 – Consider measuring CK isoenzymes as clinically indicated 	
If CK isoenzymes are abnormal
 
 – Consider checking troponin levels – Consider other assessments (including uromyoglobin) as clinically indicated 
If CK isoenzymes are normal
 
 – Continue dosing, per protocol – Monitor CK level as clinically indicated
CK or LDH > 15 to \leq 20 xULN	
 – Delay cabiralizumab and nivolumab therapy per protocol^a – Measure CK isoenzyme panel to identify source of elevation – Increase frequency of monitoring (every 48-72 hours, or more, as clinically indicated) – Notify the Medical Monitor 	
If returns to \leq 15 xULN within \leq 28 days:
 
 – Resume routine monitoring, resume cabiralizumab and nivolumab therapy at same dose level per protocol – If CK isoenzyme panel is normal continue monitoring the subject. – If CK isoenzyme panel is abnormal then consider measuring troponins. – If troponins are abnormal, contact Medical Monitor to determine if the subject can be retreated. 
If elevations persist at the same level > 28 days or worsen:
 
 – Discontinue further dosing – Discuss with Medical Monitor
CK or LDH > 20 xULN	
 – Discontinue cabiralizumab and nivolumab therapy 	
 – Follow up until resolution

a. If the AE requiring dose delay was due to one of the study drugs, the non-offending drug may be continued, taking into account the safety and clinical benefit to the patient.

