S: If 6 or more subjects have already enrolled at this dose level, accept the current dose level (4 mg/kg). Otherwise, stay current dose and enroll 3 additional subjects.

D: De-escalate to the lower dose level (2 mg/kg). Accept the lower dose level (2 mg/kg) if 6 or more subjects have already been enrolled at the lower dose level (2 mg/kg).

DU: The current dose is unacceptably toxic. De-escalate to the lower dose level (2 mg/kg) without re-escalation to the current dose level (4 mg/kg). Accept the lower dose level (2 mg/kg) if 6 or more subjects have already been enrolled at the lower dose level (2 mg/kg).

5.1.1.1 *Dose Limiting Toxicity*

Non-Hematologic DLT

A DLT is defined as a study drug-related Non-Hematologic \geq Grade 3 AE (using National Cancer Institute [NCI] Common Terminology Criteria for Adverse Events [CTCAE] v 4.0) occurring during the first 28-days, excluding:

- Grade 3 tumor flare (defined as local pain, irritation, or rash localized at sites of known or suspected tumor),
- Grade 3 rash,
- Grade 3 immune-related adverse event (irAE) that resolved to a Grade 1 or less within 14 days, or a transient (resolving within 6 hours of onset) Grade 3 infusion-related AE.
- Grade 3 or 4 increase in amylase and/or lipase that is not associated with symptoms or clinical manifestations of pancreatitis.
- In the absence of clinical symptoms and other accompanying changes in bilirubin or ALT (as noted in [appendices 6, 7 and 8](#)), serum elevations of AST/ALT $> 12 \times \text{ULN}$ and $\leq 20 \times \text{ULN}$ that last for < 7 days will not be considered a DLT and serum elevations of CK and/or LDH $> 15 \times \text{ULN}$ and $\leq 20 \times \text{ULN}$ that last for < 7 days will not be considered a DLT.

Any recurrence of Grade 3 rash, Grade 3 immune-related AE, or Grade 3 infusion-related AE will be considered a DLT. An irAE is defined as a clinically significant AE that is associated with study drug exposure, of unknown etiology, and is consistent with an immune-mediated mechanism.

Definition of Hematologic DLT

Any of the following study drug-related AEs will be considered a hematologic DLT:

- Febrile neutropenia meeting the following criteria: body temperature $\geq 38.3^{\circ}\text{C}$ at a single measurement, or hyperthermia $\geq 38^{\circ}\text{C}$ with duration ≥ 1 hour AND neutrophil count $< 500/\text{mm}^3$ or $< 1,000/\text{mm}^3$ and predicted to decrease to $< 500/\text{mm}^3$ within 48 hours

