8.1.1 Dose Discontinuation Criteria for Cabiralizumab and Nivolumab

Discontinuation rules may be different for monotherapy and combination therapy and not all rules will apply to both arms of the study. For comprehensive discontinuation rules, refer to [Appendix 6](#) (monotherapy) and [Appendix 7](#) (combination therapy) or [Appendix 8](#) (laboratory abnormalities).

Treatment of cabiralizumab in monotherapy or cabiralizumab in combination with nivolumab should be discontinued in the following cases unless otherwise specified:

- Any Grade 3 or higher uveitis *or* any Grade 2 drug-related uveitis, eye pain, or blurred vision that does not respond to topical therapy and does not improve to Grade 1 within the second re-treatment period *or* that requires systemic treatment

- Any Grade 3 or higher infusion-related reactions and hypersensitivity requiring discontinuation. Any re-initiation of therapy in this circumstance would require consultation with the Sponsor's Medical Monitor or designee.
- Any Grade 3 non-skin, drug-related AE lasting >7 days, including drug-related uveitis, pneumonitis, hypoxia, bronchospasm, and endocrinopathies with the following exceptions:
 - Grade 3 drug-related endocrinopathies adequately controlled with only physiologic hormone replacement do not require discontinuation
 - Grade 3 drug-related laboratory abnormalities do not require treatment discontinuation except:
 - Grade 3 drug-related thrombocytopenia >7 days or associated with Grade ≥ 2 bleeding requires discontinuation
- Any drug-related liver function test (LFT) abnormality that meets any one of the following criteria requires discontinuation:
 - ALT or AST $>3x$ ULN **and** total bilirubin $>2x$ ULN **or** INR $>1.5 \times$ ULN (in the absence of anticoagulation).
 - See [Appendix 6](#) and [Appendix 7](#) for guidelines and possibility of restarting therapy
 - ALT or AST $>20x$ ULN (with or without concurrent liver metastases)
 - Total bilirubin $>3x$ ULN ($>5x$ ULN with concurrent liver metastases)
- Any Grade 4 drug-related AE or laboratory abnormality, except for the following events which do not require discontinuation:
 - Grade 4 neutropenia <7 days
 - Grade 4 lymphopenia or leukopenia <7 days
 - Isolated Grade 4 amylase or lipase abnormalities that are not associated with symptoms or clinical manifestations of pancreatitis. The Sponsor's Medical Monitor or designee should be consulted for Grade 4 amylase or lipase abnormalities.

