 - Isolated Grade 4 electrolyte imbalances/abnormalities that are not associated with clinical sequelae and are corrected with supplementation/appropriate management within 72 hours of their onset
 - Grade 4 drug-related endocrinopathy AEs, such as adrenal insufficiency, adrenocorticotropic hormone (ACTH) deficiency, hyper- or hypothyroidism, or glucose intolerance, which resolve or are adequately controlled with physiologic hormone replacement (corticosteroids, thyroid hormones) or glucose-controlling agents, respectively, may not require discontinuation after discussion with and approval from the Sponsor's Medical Monitor or designee.
 - Grade 4 CK up to $20 \times$ ULN (in the absence of clinical sequelae)
- Any event that leads to delay in dosing lasting >6 weeks from the previous dose requires discontinuation, with the following exceptions:
 - Dosing delays to manage drug-related adverse events are allowed. Prior to re-initiating treatment in a patient with a dosing delay lasting >6 weeks from the previous dose, the Sponsor's Medical Monitor or designee must be consulted. Tumor assessments should continue as per-protocol even if dosing is delayed. Periodic study visits to assess safety and laboratory studies should also continue per protocol, or more frequently if clinically indicated during such dosing delays or per the Investigator's discretion.
 - Dosing delays lasting >6 weeks from the previous dose that occur for non-drug-related reasons may be allowed if approved by the Sponsor's Medical Monitor or designee.

Prior to re-initiating treatment in a patient with a dosing delay lasting >6 weeks, the Sponsor's Medical Monitor must be consulted. Tumor assessments should continue per protocol every 8 weeks (± 7 days) even if dosing is delayed. Periodic study visits to assess safety and laboratory studies should also continue per-protocol or more frequently if clinically indicated during such dosing delays or per the Investigator's discretion.

- Any AE, laboratory abnormality, or intercurrent illness which, in the opinion of the Investigator, presents a substantial clinical risk to the patient with continued cabiralizumab and/or nivolumab dosing
- Any Grade 3 or higher neurological toxicity
- Any Grade 3 or higher periorbital edema and persistent Grade 2 periorbital edema requiring 2 missed doses unless approved by Sponsor's Medical Monitor

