APPENDIX 6 AE MANAGEMENT FOR CABIRALIZUMAB MONOTHERAPY COHORTS

Hepatic Adverse Event Management without Liver Metastasis		
Grade of Liver Test Elevation	Management	Follow-Up
AST or ALT $>3.0 \times \text{ULN}$ and Total bilirubin $>2 \times \text{ULN}$ or INR > 1.5	
 – Discontinue cabiralizumab therapy per protocol 	
 – Continue LFT monitoring per protocol until resolution. – Continue monitoring for and other associated clinical signs or symptoms – Contact the Medical Monitor – Evaluate for non-drug related causes of the laboratory abnormalities (e.g. obstruction, viral infection, Gilbert's disease, etc) – Under selected circumstances (e.g alternative etiology is identified), patient may receive additional therapy only after consultation and agreement between the Sponsor/MM and the investigator if receiving additional treatment with cabiralizumab is in the best interest of the patient (e.g if the subject has demonstrated a response to therapy)
AST or ALT > 5 to $\leq 12 \times \text{ULN}$ and Total bilirubin $\leq 2 \times \text{ULN}$	
 – Continue cabiralizumab therapy if there are no clinical signs of significant muscle or hepatic damage – Increase frequency of monitoring of AST, ALT, bilirubin, alkaline phosphatase and INR (every 48-72 hours or more frequently, as clinically indicated) – Monitor for other clinical symptoms (fatigue, nausea, vomiting, abdominal pain, fever, rash, and/or eosinophilia) 	
 – Contact the Medical Monitor if there are clinical signs of muscle or hepatic injury or other clinical symptoms – Contact the Medical Monitor if there is a concurrent increase of bilirubin, AST, ALT, or alkaline phosphatase from baseline. – Notify the Medical Monitor if there is an AST increase $> 5 \times \text{ULN}$ – Frequency of retesting can decrease to once a week or less if abnormalities stabilize or the trial drug has been discontinued and the subject is asymptomatic – Consider gastroenterology or hepatology referral

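### For drug-related Grade 4 CK above 15 and up to 20 x ULN with clinical sequelae, Section 8.1.1 calls for discontinuation, but the Appendix 8 row, read on its own, leads to delay and restart

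*Protocol*

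**What the plan says.** Section 8.1.1 states that treatment "should be discontinued in the following cases unless otherwise specified". One listed case is "Any Grade 4 drug-related AE or laboratory abnormality, except for the following events which do not require discontinuation". Grade 4 CK up to 20 x ULN is among the exceptions, on condition that it occurs "in the absence of clinical sequelae". The same section opens with "For comprehensive discontinuation rules, refer to" Appendices 6, 7 and 8, the last being for laboratory abnormalities.

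Appendix 8 has a row for CK or LDH above 15 and up to 20 x ULN. Its Management column orders a delay, a CK isoenzyme panel, more frequent monitoring and notification of the Medical Monitor. Its Follow-Up column says that on return to 15 x ULN or less within 28 days the action is "Resume routine monitoring, resume cabiralizumab and nivolumab therapy at same dose level per protocol". Further dosing stops if the elevation persists beyond 28 days or worsens. An abnormal isoenzyme panel leads to considering troponins, and then: "If troponins are abnormal, contact Medical Monitor to determine if the subject can be retreated". The table does not mention symptoms or clinical sequelae.

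Section 7.4.2 makes the appendix tables, including Appendix 8, the reference for resuming treatment. Section 7.4.3 does not permit dose reduction.

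**The concern.** The two texts share an upper limit of 20 x ULN, but only one of them asks whether the patient has clinical consequences of the CK rise. If a site uses the appendix as its working table, a patient with a symptomatic Grade 4 CK rise could be rechallenged at the full dose when Section 8.1.1 would have ended treatment. The SAP (Section 7.1.1.1) lists CK abnormality, myositis, myocarditis and rhabdomyolysis as events of interest, so muscle and cardiac sequelae are foreseen.

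There is a smaller effect on reporting. SAP Section 7.1.1 classifies an adverse event as leading to discontinuation or to dose delay from the recorded action taken. The same clinical event would fall in different categories according to which text the site followed. Adverse events leading to discontinuation belong to the primary endpoint in the monotherapy cohorts and to a secondary endpoint in the combination cohorts.

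**Working it through.** The plan gives no figure to reproduce, so the check is a comparison of texts.

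**Step 1: where Grade 4 CK starts.** The documents give no CTCAE cut-off. The exception for Grade 4 CK up to 20 x ULN implies that Grade 4 begins below 20 x ULN. Its exact start has to be assumed:
- At or below 15 x ULN: the whole row above 15 and up to 20 x ULN is affected.
- Between 15 and 20 x ULN: only the part of the row above the cut-off is affected.
- Below 15 x ULN: the CK > 10 x ULN row is also affected where the value is Grade 4. That row continues dosing if isoenzymes are normal and sets no condition on sequelae.

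**Step 2: the instruction in each case, for drug-related Grade 4 CK.**

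| Case | Section 8.1.1, Grade 4 rule | Appendix 8, read alone | Result |
|---|---|---|---|
| >15 to ≤20 x ULN, no sequelae, falls to ≤15 within 28 days | Discontinuation not required | Delay, then resume at same dose | Compatible |
| >15 to ≤20 x ULN, with sequelae, falls to ≤15 within 28 days | Discontinue | Delay, then resume at same dose | Conflict |
| >15 to ≤20 x ULN, with sequelae, persists >28 days or worsens | Discontinue | Delay, then discontinue | Same end, reached later |
| >20 x ULN | Discontinue | Discontinue | Agree |

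The conflict is the second line. LDH is not part of it, because the Section 8.1.1 exception names CK only.

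**Step 3: precedence.** Three pointers favour Appendix 8: the proviso in Section 8.1.1 ("should be discontinued in the following cases unless otherwise specified"), its description of the appendices as comprehensive, and the reference in Section 7.4.2. One points the other way: the delay and resume lines in the row both end with *per protocol*, which can be read as bringing Section 8.1.1 back in. If Appendix 8 prevailed, the condition on sequelae in Section 8.1.1 would have no effect in this band. No statement settles the order.

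**Step 4: the DLT rule for the same band.** In Section 5.1.1.1 the bullet that excludes short CK or LDH elevations above 15 and up to 20 x ULN from being a DLT opens "In the absence of clinical symptoms and other accompanying changes in bilirubin or ALT". There, clinical symptoms do matter for the same CK values.

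**Step 5: what remains uncovered.** A drug-related sequela that is itself Grade 4, or non-skin Grade 3 lasting more than 7 days, stops treatment under Section 8.1.1 in its own right, subject to the listed exceptions. What remains is mainly lower-grade or shorter-lived sequelae in a subject whose CK falls to 15 x ULN or less within 28 days.

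**The case against.** The strongest reply is that the texts can be followed together. Appendix 8 is a table of laboratory values. Nothing in it says to resume despite sequelae, and its lines say *per protocol*. Section 7.4.2 is permissive and ties resumption to resolution of the adverse event. On this reading the CK value allows a restart and the sequelae bar it under Section 8.1.1. This stands in part. A reader might infer that a site cannot comply with both texts, or that the protocol orders rechallenge of a symptomatic patient; the documents do not support either claim. They do leave a table that, used alone, leads to a restart, with pointers that run in both directions.

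A reader might also infer that Appendix 8 is the odd one out, since the Appendix 6 hepatic table says "Continue cabiralizumab therapy if there are no clinical signs of significant muscle or hepatic damage". That line governs continuing without a hold at AST or ALT above 5 and up to 12 x ULN. The parallel hepatic row, a delay at above 12 and up to 20 x ULN, orders symptom monitoring but sets no absence-of-symptoms condition for resuming. Appendix 8 follows that pattern. The conflict arises because Section 8.1.1 attaches a specific condition to CK.

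Finally, safeguards remain. Medical Monitor notification is unconditional in the row. Section 8.1 requires discontinuation where the investigator judges that continuing is not in the participant's best interest, and Section 8.1.1 has a similar clause on substantial clinical risk. Section 9 requires immediate safety concerns to be discussed with the sponsor. These reduce the practical risk. They rest on judgement or consultation, however, and do not restate the fixed stopping rule.

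**Conclusion.** The safety rule is wrong as written, in that it conflicts internally, and the severity is minor. For drug-related Grade 4 CK above 15 and up to 20 x ULN with clinical sequelae, Section 8.1.1 calls for discontinuation. The matching Appendix 8 row, read on its own, directs delay and then full-dose resumption once CK is at 15 x ULN or less within 28 days. Which text governs is unclear.

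The conclusion assumes that some or all of this CK band is Grade 4, which Section 8.1.1 implies without giving a cut-off. No numerical size is attached. The visible text does not give the frequency of such CK rises. A reader might infer a large effect on the discontinuation endpoint because the cohorts are small, but one subject moves any incidence by 1/n whatever the event, so that says nothing specific about this gap.

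**What to change.** In Appendix 8, row CK or LDH > 15 to ≤ 20 x ULN, add as the first Management line: *Drug-related Grade 4 CK with clinical sequelae: discontinue per Section 8.1.1; the delay/resume lines below apply to CK only in the absence of clinical sequelae.* Apply the same line to the CK > 10 x ULN row where the CK is Grade 4, adapted to that row's continue-dosing instruction.

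The cost is a wording edit in one appendix table. The stopping condition is already in Section 8.1.1, so no visit, test or dosing hold is added. The LDH instructions and the troponin line can stay as they are.

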APPENDIX 9 ECOG PERFORMANCE STATUS

ECOG PERFORMANCE STATUS ^a	
0	Fully active, able to carry on all pre-disease performance without restriction
1	Restricted in physically strenuous activity but ambulatory and able to carry out work of a light or sedentary nature, eg, light house work, office work
2	Ambulatory and capable of all selfcare but unable to carry out any work activities. Up and about more than 50% of waking hours
3	Capable of only limited selfcare, confined to bed or chair more than 50% of waking hours
4	Completely disabled. Cannot carry on any selfcare. Totally confined to bed or chair
5	Dead

a [REDACTED]

APPENDIX 10 RESPONSE CRITERIA (RECIST 1.1)

1 EVALUATION OF LESIONS

At baseline, tumor lesions/lymph nodes will be categorized measurable or non-measurable as follows:

1.1 Measurable

Tumor lesions: Must be accurately measured in at least one dimension (longest diameter in the plane of measurement is to be recorded) with a minimum size of:

1. 10 mm by CT scan (CT scan slice thickness no greater than 5 mm)
2. 10 mm caliper measurement by clinical exam (lesions which cannot be accurately measured with calipers should be recorded as non-measurable)
3. 20 mm by chest x-ray

Malignant lymph nodes: To be considered pathologically enlarged and measurable, a lymph node must be ≥ 15 mm in short axis when assessed by CT scan (CT scan slice thickness recommended to be no greater than 5 mm).

Lymph nodes merit special mention since they are normal anatomical structures which may be visible by imaging even if not involved by tumor. Pathological nodes which are defined as measurable and may be identified as target lesions must meet the criterion of a short axis of ≥ 15 mm by CT scan. Only the short axis of these nodes will contribute to the baseline sum. The short axis of the node is the diameter normally used by radiologists to judge if a node is involved by solid tumor. Nodal size is normally reported as two dimensions in the plane in which the image is obtained (for CT scan this is almost always the axial plane; for MRI the plane of acquisition may be axial, sagittal or coronal). The smaller of these measures is the short axis. For example, an abdominal node which is reported as being 20 mm x 30 mm has a short axis of 20 mm and qualifies as a malignant, measurable node. In this example, 20 mm should be recorded as the node measurement. All other pathological nodes (those with short axis ≥ 10 mm but < 15 mm) should be considered non-target lesions. Nodes that have a short axis < 10 mm are considered non-pathological and should not be recorded or followed.

1.2 Non-Measurable

All other lesions are considered non-measurable, including small lesions (longest diameter < 10 mm or pathological lymph nodes with ≥ 10 to < 15 mm short axis) as well as truly non-measurable lesions. Lesions considered truly non-measurable include: leptomeningeal disease, ascites, pleural or pericardial effusion, inflammatory breast disease, lymphangitic involvement of skin or lung, abdominal masses/abdominal organomegaly identified by physical exam that is not measurable by reproducible imaging techniques.

2 BASELINE DOCUMENTATION OF 'TARGET' AND 'NON-TARGET' LESIONS

When more than one measurable lesion is present at baseline all lesions up to a maximum of five lesions total (and a maximum of two lesions per organ) representative of all involved organs should be identified as target lesions and will be recorded and measured at baseline (this means in instances where patients have only one or two organ sites involved a maximum of two and four lesions respectively will be recorded).

Target lesions should be selected on the basis of their size (lesions with the longest diameter), be representative of all involved organs, but in addition should be those that lend themselves to reproducible repeated measurements. It may be the case that, on occasion, the largest lesion does not lend itself to reproducible measurement in which circumstance the next largest lesion which can be measured reproducibly should be selected.

A sum of the diameters (longest for non-nodal lesions, short axis for nodal lesions) for all target lesions will be calculated and reported as the baseline sum diameters. If lymph nodes are to be included in the sum, then as noted above, only the short axis is added into the sum. The baseline sum diameters will be used as reference to further characterize any objective tumor regression in the measurable dimension of the disease.

All other lesions (or sites of disease) including pathological lymph nodes should be identified as non-target lesions and should also be recorded at baseline. Measurements are not required and these lesions should be followed as 'present', 'absent', or in rare cases 'unequivocal progression' (more details to follow). In addition, it is possible to record multiple nontarget lesions involving the same organ as a single item on the case record form (eg, 'multiple enlarged pelvic lymph nodes' or 'multiple liver metastases').

